### **10.1.3 Recording and Reporting of Serious Adverse Events**

Every SAE (regardless of severity and causality) that occurs once the caregiver/patient has signed the ICF and until the post-treatment follow-up (Visit 10), and 28 days after the final dose of study drug, should immediately and not later than within 24 hours of knowledge of the event, be reported by the investigator or delegate in the SAE report form.

Report of a SAE must include at least the following information:

- Patient identification information (study number, site number, initials, and date of birth [as per local country requirements for data protection])
- The last study drug administration date
- The diagnosis of the event with the description (or a brief description of signs/symptoms/clinical course if the diagnosis is not available) and the date of onset
- The action used to treat the event (i.e., treatment medications, temporary discontinuation)
- The reason(s) for considering the event serious
- The relationship of the event to the study drug or to the study procedure (e.g., the investigator's assessment of causality)
- A brief narrative of the SAE

Follow-up reports including all new information obtained of the subsequent course of the SAE must be prepared and the information collected in the SAE submitted to [REDACTED] (Pharmacovigilance and Safety Services Department) by e-mail within 24 hours of knowledge of the event.

The pharmacovigilance manager (PVM) may contact the investigator to obtain further information on a reported SAE. The investigator/investigative staff must respond to any

request for follow-up information or answers to questions regarding the SAE within the same timelines as for initial reports.

The PVM reports the occurrence of the SAE and follow-up to the Albireo medical monitor for medical assessment of the case.

Should an outcome of death occur within the study period or within 28 days after the last administration of study drug, an SAE form should be completed including the main and contributory causes of death.

All SAE reports must be e-mailed to the following e-mail address within **24 hours**:

[REDACTED]

[REDACTED]

If email is unavailable, SAEs may be transmitted via fax to the following number:

[REDACTED]

In a study-related medical emergency situation, when the assigned medical monitors for the study cannot be reached by a caller, an on call physician can be reached 24 hours per day, 7 days per week, via the [REDACTED] call center. The following number is a chargeable telephone number allowing a global reach from both landlines and mobile phones and the internet page indicated below contains a list of country-specific toll-free telephone numbers that is provided. It should be noted that not all countries globally have access to toll-free numbers as indicated on the “24/7 Medical Help desk” index. Countries without toll-free numbers need to dial the chargeable number as indicated below. Furthermore, toll-free numbers might not be available from mobile phones.

[REDACTED]

[REDACTED]

#### **10.1.4 Reporting of Suspected Unexpected Serious Adverse Reactions**

Suspected unexpected serious adverse reaction (SUSAR) is an SAE that occurs in a patient, the nature or severity of which is not expected per the applicable product information (e.g., the IB for an unauthorized investigational product or summary of product characteristics for an authorized product).

Reporting and tracking of SUSARs will be in accordance to all applicable competent authority regulations. The Ethics Committee and all investigators involved in this study will be informed according to national and international requirements.

## **10.2 Laboratory Values/Vital Signs/Physical Examinations and Other Safety Assessments**

### **10.2.1 Laboratory Assessments**

Samples will be collected for clinical chemistry, hematology, and urinalysis testing at the time points specified in [Table 1](#). The parameters assessed are presented in [Table 3](#).

Blood for AFP will be drawn at Visits 3 and 9. Fat-soluble vitamin levels including vitamins A and E, and 25-hydroxy vitamin D will be drawn at Visit 2 (vitamins A & E only), Visit 3 (25-hydroxy vitamin D only), Visit 6, and Visit 9. Blood for INR (surrogate for vitamin K) will be drawn at Visits 2, 4, 6, 8, and 10. Patients will fast (water intake only is permissible) for at least 4 hours prior to the collection of samples for vitamin A. Exceptions can be made for infants, <12 months of age, if unable to fast for the full 4 hours. If a patient has any vitamin level(s) that are outside of the reference range, vitamin supplementation adjustments may be required. Target ranges and supplementation strategy guidelines can be found in [Appendix 5](#).

A serum pregnancy test will be performed at Visit 1 and Visit 9 if the patient is entering the A4250-008 study. A urine pregnancy test will be collected at all other visits for girls who have reached menarche. If a urine pregnancy test is positive, a serum pregnancy test should be performed to confirm the pregnancy. Study drug administration will be held pending the confirmatory results. If the serum pregnancy test is negative, the patient can resume dosing. If the serum pregnancy test is positive, the patient should be discontinued (see [Section 10.2.9](#)).

All samples will be processed and transported to a laboratory per instructions in the laboratory manual.

The observed values will be recorded and assessed as “normal” or “abnormal not clinically significant” or “abnormal clinically significant”.

Additional safety blood samples may be needed due to follow-up of an abnormal value or analysis failure. The blood samples collected for safety laboratory analysis will be destroyed after the analyses have been completed.

**Table 3 Routine Laboratory Parameters**

Clinical Chemistry	Hematology	Urinalysis

 
• Albumin
 
• ALT
 
• Alkaline phosphatase
 
• AST
 
• Bilirubin – total and direct
 
• Calcium
 
• Chloride
 
• Creatinine
 
• Creatine kinase
 
• Gamma-glutamyl transferase
 
• Potassium
 
• Sodium
 
	
 
• Hematocrit
 
• Hemoglobin
 
• Platelet count
 
• Red blood cell count
 
• White blood cell count and differential (neutrophils, eosinophils, basophils, lymphocytes, and monocytes)
 
	
 
• Blood
 
• Glucose
 
• Ketones
 
• Leukocytes
 
• Nitrites
 
• pH
 
• Protein
 

## 10.2.2 Individual Patient Safety Monitoring

### 10.2.2.1 Liver Monitoring

Strategies to monitor markers of liver disease throughout the study are outlined below where the ULN will be based on central laboratory reference values for age and gender.

**If isolated transaminase elevations are observed, defined as:**

1. Normal bilirubin AND absence of clinical hepatitis symptoms AND
  - ALT or AST  $\geq 5 \times$  ULN (if normal at baseline) or an absolute threshold of 800 U/L, whichever comes first
  - OR ALT or AST  $\geq 3 \times$  baseline (if abnormal at baseline) or an absolute threshold of 800 U/L, whichever comes first

Then:

- a) Repeat liver profile (AST, ALT, bilirubin, and prothrombin time [PT] or INR) within 2 to 3 days
- b) Evaluate creatine phosphokinase (CPK) and lactate dehydrogenase (LDH)
- c) As needed (for example, persistent ALT/total bilirubin elevation or worsening of liver function), consider evaluation for alternative etiologies

Monitor the patient using close observation found in [Section 10.2.2.2](#)

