**If any ONE of the following criteria are met:**

1. Transaminases (ALT or AST  $\geq 3 \times$  baseline or 800 U/L, whichever comes first) AND bilirubin (total bilirubin  $> 2 \times$  ULN) elevations

2. Transaminase elevations alone (ALT or AST  $>10 \times$  ULN or  $5 \times$  baseline or absolute threshold of 800 U/L, whichever comes first) in presence of normal LDH and CPK
3. Total bilirubin increased, unrelated to hemolysis (elevated reticulocyte count) or established genetic diseases, such as Gilbert's syndrome
  - a. Doubling if total bilirubin was  $<3$  mg/dL (equivalent to  $51.3 \mu\text{mol/L}$ ) at baseline
  - b. OR Increase by  $>3$  mg/dL (equivalent to  $51.3 \mu\text{mol/L}$ ) if total bilirubin was  $\geq 3$  mg/dL (equivalent to  $51.3 \mu\text{mol/L}$ ) at baseline
4. INR increase refractory to vitamin K administration
  - a. INR  $>1.5$  if INR was normal at baseline
  - b. OR Increase by  $>0.4$  if INR was abnormal at baseline
5. Any increase in total bilirubin and transaminases if accompanied by EITHER a symptom of clinical hepatitis (e.g., vomiting, nausea, right upper quadrant pain) OR immunological reaction (rash or  $>5\%$  eosinophilia)

Then:

- a) Interrupt study medication
- b) Initiate drug-induced liver injury work-up for alternative etiologies
- c) Repeat liver profile (AST, ALT, total bilirubin, direct bilirubin) and PT or INR within 48 to 72 hours
- d) Monitor the patient using close observation found in Section 10.2.2.2
- e) If a patient lives in a remote area, they may be tested locally and the results communicated to the investigator site promptly

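### Section 10.2.2.1: with a baseline ALT or AST of >1x to <3.33x ULN, a rise to 3x to <5x baseline (≤10x ULN, <800 U/L) can enter neither liver tier if bilirubin is mildly raised, or if a hepatitis symptom occurs with normal, stable bilirubin

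*Protocol*

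**What the plan says.** Protocol section 10.2.2.1 (Liver Monitoring) sets two tiers.

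The first leads to close observation. Its entry conditions are "Normal bilirubin AND absence of clinical hepatitis symptoms AND" an enzyme threshold. For a child with abnormal baseline values the threshold is ALT or AST of at least 3x baseline, or 800 U/L if that is reached first. The steps that follow include "Repeat liver profile (AST, ALT, bilirubin, and prothrombin time [PT] or INR) within 2 to 3 days" and "Evaluate creatine phosphokinase (CPK) and lactate dehydrogenase (LDH".

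The second tier interrupts study drug if any one of five criteria is met:

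1. ALT or AST at least 3x baseline (or 800 U/L), together with total bilirubin above 2x ULN.
2. "Transaminase elevations alone": above 10x ULN, or 5x baseline, or the "absolute threshold of 800 U/L, whichever comes first) in presence of normal LDH and CPK".
3. A bilirubin increase: "Doubling if total bilirubin was" under 3 mg/dL at baseline, otherwise a rise of more than 3 mg/dL.
4. An INR increase that does not respond to vitamin K.
5. "Any increase in total bilirubin and transaminases if accompanied by EITHER a symptom of clinical hepatitis" or an immunological reaction (rash, or eosinophilia above 5%).

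After interruption the protocol asks for "Repeat liver profile (AST, ALT, total bilirubin, direct bilirubin) and PT or INR within 48 to 72 hours".

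**The concern.** The two tiers do not adjoin. Observation stops as soon as bilirubin exceeds normal, while the matching interruption criterion begins only above 2x ULN. Observation also stops as soon as a hepatitis symptom appears, while the symptom-based interruption criterion needs bilirubin to rise as well. Between these edges a marked transaminase rise can meet no rule.

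The order is also the wrong way round. A child with pain, or with bilirubin at 1.5x ULN, gets less mandated follow-up than an otherwise identical child without it. Fixed triggers exist so that the response to a liver signal does not vary by site, and here the written rule is silent for the child who looks slightly worse.

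Mildly raised bilirubin is plausible in this trial. Section 5.2.1, in the earlier protocol version bound in the same file, describes raised bilirubin with raised ALT and AST as part of the disease. Exclusion criterion 14 in section 7.2.2 bars entry only above 5x ULN.

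**Working it through.** **Inputs.** All rules come from section 10.2.2.1. Chemistry days come from Table 1 and section 7.1.3.2. Let b be baseline ALT or AST (b > 1, abnormal), and c and d be baseline and current bilirubin, all in multiples of ULN.

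**Rules as conditions**
- Observation: ALT or AST ≥ 3b, and d ≤ 1, and no symptom.
- Criterion 1: ALT or AST ≥ 3b, and d > 2.
- Criterion 2 level: ALT or AST > 10, or ≥ 5b, or ≥ 800 U/L.
- Criterion 3: d ≥ 2c if baseline bilirubin is below 3 mg/dL, otherwise a rise above 3 mg/dL.
- Criterion 5: d > c, with a symptom or immunological reaction.

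**Enzyme range below the criterion 2 level.** The value must be at least 3b, below 5b, and at or below 10. The range closes when 3b = 10, so at b = 10/3 = 3.33.

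| Baseline (x ULN) | 3x baseline | 5x baseline | Range that can be uncovered (x ULN) |
|---|---|---|---|
| 1.2 | 3.6 | 6.0 | 3.6 to <6.0 |
| 1.5 | 4.5 | 7.5 | 4.5 to <7.5 |
| 2.0 | 6.0 | 10.0 | 6.0 to <10.0 |
| 2.5 | 7.5 | 12.5 | 7.5 to 10.0 |
| 3.0 | 9.0 | 15.0 | 9.0 to 10.0 |
| 4.0 | 12.0 | 20.0 | none: 12.0 > 10 |

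The protocol gives no ALT or AST ULN. If it is 30, 40 or 60 U/L, 10x ULN is 300, 400 or 600 U/L. The 800 U/L limit could cut into the range only if ULN exceeded 800/10 = 80 U/L.

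**Bilirubin and symptom states that leave this range uncovered** (criterion 4 not met)
- (i) d >1 to 2, with criteria 3 and 5 not met. Observation fails because d > 1, and criterion 1 fails because d ≤ 2. If baseline bilirubin is already above ULN, doubling would take it above 2x ULN, so the doubling rule cannot fire in this band. If baseline was normal it can: 0.6 to 1.2 is a doubling, and criterion 3 then interrupts.
- (ii) d ≤ 1, d not above c, symptom present. The symptom bars observation, and criterion 5 fails because bilirubin has not risen.

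Enumerating the rules over a 0.1x ULN grid in this range (1,662,120 combinations, bilirubin ULN assumed 1.2 mg/dL) finds no rule met in exactly states (i) and (ii). This checks the logic only. Criteria 2 and 4 are outside the grid by construction, and the counts are not patient frequencies.

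**Worked cases** (baseline ALT 2x ULN, now 8x ULN, so 8/2 = 4x baseline; INR criterion not met)
- A: bilirubin 1.2x ULN at baseline, 1.5x now (ratio 1.25), no symptom, rash or eosinophilia. No rule fires. With bilirubin at 1.0x, observation fires.
- B: bilirubin 0.8x ULN, unchanged, right upper quadrant pain. No rule fires. Without the pain, observation fires. With bilirubin at 0.81x, criterion 5 interrupts.

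**Time to the next required test.** Chemistry is scheduled on Days 0, 28, 56, 84, 126 and 168; Visit 8 (Day 154) has none. The intervals are 28, 28, 28, 42 and 42 days. With ±3-day windows the longest are 31, 34, 34, 48 and 48 days. Observation requires a repeat in 2 to 3 days.

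**LDH.** Criterion 2 needs normal LDH and CPK. Table 3 lists creatine kinase but not LDH. LDH is ordered only in step b of the observation tier. It is absent from the interruption tier's repeat profile and from section 10.2.2.2. A child in state (i) or (ii) who passes the criterion 2 level (as A, but ALT 11x ULN, 5.5x baseline) therefore depends on a result that no step orders for that child.

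**The case against.** The affected slice needs several things at once: a baseline above 1x and below 3.33x ULN, a rise within a limited band, no INR event, and one of two bilirubin or symptom states. The protocol gives no baseline distribution, and neither the disease description nor the 5x ULN entry limit places patients specifically at 1x to 2x ULN. This stands, and no share of patients is claimed.

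A child in the gap is not unreviewed. Investigators grade each laboratory value and may take extra samples (section 10.2.1), judge whether a change is an adverse event (10.1.2), and may withdraw the patient (7.2.3). The DSMB meets about quarterly (11.2.4). These soften the gap, but none of them sets a repeat test or a deadline.

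A reader might infer that every rise to 3x to 5x an abnormal baseline is uncovered in these states. The documents do not support that. Entry allows ALT up to 10x ULN, and above a 3.33x ULN baseline a 3x rise already passes 10x ULN and reaches the criterion 2 level.

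A reader might also take the word alone in criterion 2 to exclude raised bilirubin, which would leave state (i) uncovered at much higher ALT. Next to criterion 1, which pairs transaminases with bilirubin, the more natural meaning is that no bilirubin condition is needed. The stricter reading is not relied on. Nor is LDH unobtainable: a criterion that turns on it implies the test, and the laboratory manual is not shown. The defect is that section 10.2.2.1 orders LDH only for children who enter observation.

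**Conclusion.** The gap holds within stated limits. It covers abnormal baseline ALT or AST below 3.33x ULN and a value of at least 3x but below 5x baseline, at or below 10x ULN and below 800 U/L, with criteria 3, 4 and 5 not met. Bilirubin must be >1x to 2x ULN, or normal and not rising with a hepatitis symptom. Inside those limits the required interval to the next chemistry is 28 or 42 days instead of 2 to 3. The bounds follow from the protocol's own thresholds; only the statement that 800 U/L does not cut in rests on an assumption, a ULN of at most 80 U/L. The dependence of criterion 2 on LDH is a separate, smaller fault.

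This is more than missing detail, because following the rules as written mandates less for the child with the additional finding. Clinical discretion limits the harm and the frequency is unknown, so it ranks as a cheap improvement to a safety rule.

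**What to change.** Amend section 10.2.2.1 in two places.

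(a) Remove the normal-bilirubin and no-symptom conditions from the observation tier and reword its heading, which now calls the elevations isolated. Any ALT or AST at the observation threshold that meets no interruption criterion then gets the repeat profile within 2 to 3 days and close observation.

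(b) Order LDH and CPK whenever ALT or AST reaches a threshold in either tier.

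Cases A and B then enter observation. At 11x ULN the LDH and CPK results decide between interruption under criterion 2 and observation. Numeric thresholds and interruption criteria do not change. Whether a symptomatic child with stable bilirubin should instead be interrupted is a clinical choice that this change leaves open.

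The cost is a short amendment, a matching laboratory manual entry, and an added LDH assay on blood already drawn for the repeat profile. The downside is a few more assays and observation episodes, including in children with chronically raised bilirubin.

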**If any ONE of the following criteria are met:**

1. Transaminases (ALT or AST  $\geq 3 \times$  baseline or 800 U/L, whichever comes first) AND bilirubin (total bilirubin  $> 2 \times$  ULN) elevations

2. Transaminase elevations alone (ALT or AST  $>10 \times$  ULN or  $5 \times$  baseline or absolute threshold of 800 U/L, whichever comes first) in presence of normal LDH and CPK
3. Total bilirubin increased, unrelated to hemolysis (elevated reticulocyte count) or established genetic diseases, such as Gilbert's syndrome
  - a. Doubling if total bilirubin was  $<3$  mg/dL (equivalent to  $51.3 \mu\text{mol/L}$ ) at baseline
  - b. OR Increase by  $>3$  mg/dL (equivalent to  $51.3 \mu\text{mol/L}$ ) if total bilirubin was  $\geq 3$  mg/dL (equivalent to  $51.3 \mu\text{mol/L}$ ) at baseline
4. INR increase refractory to vitamin K administration
  - a. INR  $>1.5$  if INR was normal at baseline
  - b. OR Increase by  $>0.4$  if INR was abnormal at baseline
5. Any increase in total bilirubin and transaminases if accompanied by EITHER a symptom of clinical hepatitis (e.g., vomiting, nausea, right upper quadrant pain) OR immunological reaction (rash or  $>5\%$  eosinophilia)

Then:

- a) Interrupt study medication
- b) Initiate drug-induced liver injury work-up for alternative etiologies
- c) Repeat liver profile (AST, ALT, total bilirubin, direct bilirubin) and PT or INR within 48 to 72 hours
- d) Monitor the patient using close observation found in Section 10.2.2.2
- e) If a patient lives in a remote area, they may be tested locally and the results communicated to the investigator site promptly

#### **10.2.2.2 Close Observation**

- Repeat liver enzyme and serum bilirubin tests two or three times weekly. Frequency of re-testing can decrease to once a week or less if abnormalities stabilize or the trial drug has been discontinued and the subject is asymptomatic
- Obtain a more detailed history of symptoms and prior or concurrent diseases
- Obtain a history of concomitant drug use (including non-prescription medications and herbal and dietary supplement preparations), alcohol use, recreational drug use, and special diets
- Consider ruling out alternate etiology including acute viral hepatitis types A, B, C, D, and E; autoimmune or alcoholic hepatitis; non-alcoholic steatohepatitis; hypoxic/ischemic hepatopathy; and biliary tract disease
- Obtain a history of exposure to environmental chemical agents.

- Obtain additional tests to evaluate liver function, as appropriate (e.g., INR, direct bilirubin)
- Consider gastroenterology or hepatology consultations.

### **10.2.2.3 De-challenge/Re-challenge for Liver and Clinical Hepatitis Monitoring**

1. Re-challenge is not recommended:
  - a. If a patient has had possible/probable drug-induced liver injury
  - b. If a decompensation event has occurred (i.e., variceal hemorrhage, ascites, hepatic encephalopathy, etc.).
2. If due to underlying cholestatic liver disease variability or another alternative etiology is identified AND liver tests returned to baseline, re-challenge may be considered after consultation with the sponsor Medical Monitor.
3. If the ALT/total bilirubin elevations are observed after re-challenge, then repeat re-challenge is discouraged.

If patient is permanently discontinued, monitoring should be continued as outlined in Section 10.2.2.5.

### **10.2.2.4 Diarrhea**

Study drug should be discontinued if a patient develops diarrhea with at least 1 of the following concomitant signs or symptoms: grossly bloody stools, vomiting, dehydration requiring treatment with oral or intravenous rehydration and/or electrolyte imbalances, fever ( $\geq 38$  C) and/or the diarrhea persists for 7 or more days.

If there is gross blood in stool, INR and platelets should be measured.

Study drug will be reintroduced (re-challenge) when the symptoms have resolved. If the diarrhea re-occurs within 1 week after the re-challenge with no alternate etiology, the patient will be permanently discontinued and monitored as outlined in Section 10.2.2.5.

### **10.2.2.5 Monitoring after Permanent Discontinuation of Study Drug Due to Safety**

Once study drug is permanently discontinued for liver, hepatitis, diarrhea, or other severe AE related to study drug, the patient will be monitored weekly until the laboratory and clinical parameters have normalized/stabilized.

### **10.2.3 Demographics/Medical and Surgical History**

Demographic information per country regulations (age, full date of birth, gender, race, and ethnicity), along with medical and surgical history, will be obtained and recorded in the eCRF at Visit 1.

Medical and surgical history will be entered in the eCRF at Visit 1. This includes date of diagnosis of PFIC, prior investigational medications for PFIC, historical (3 months prior to

Screening) LFT values (AST, ALT, and total bilirubin), ongoing medication, any surgery performed, any other diagnosis, and historical biopsy data.

If a liver biopsy has been performed within 1 year prior to Screening, or during the study, the results will be recorded in the eCRF.

#### **10.2.4 Clinical Genetic Testing**

For previous confirmatory clinical genetic testing results for PFIC Type 1 or 2 performed prior to Screening Visit 1, the confirmatory clinical genetic testing laboratory report will be verified to determine eligibility.

If the historical clinical genetic result is equivocal, unavailable, or unobtainable, clinical genetic analysis to confirm pathologic biallelic variations in the *ATP8B1* or *ABCB11* genes will be performed and verified to determine eligibility. No other diagnostic genetic testing will be offered.

